2.3.2 Weighted Gene Correlation Network Analysis (WGCNA)

The normalized dataset will undergo variance stabilizing transformation (vst) using the DESeq2 package, to be further explored using Weighted Gene Correlation Network Analysis (WGCNA)(4). WGCNA is an unsupervised analysis method which clusters genes into defined modules of highly interconnected genes based on the similarity of gene co-expression profiles. These modules can be assessed for correlations with specific clinical traits; specifically, we will assess whether any gene module is associated with one of the blinded treatment arms. Additionally, for each gene module, 'hub' genes can be identified, which are genes with high connectivity, and therefore high importance, within a co-expression module. Hub gene analysis and visualization of gene networks will be carried out using Cytoscape(5). Identification of these hub genes may reveal the key molecular drivers within treatment arms or relationships with clinical response.

2.3.3 Gene pathway analysis

Following the identification of DEGs, gene modules of interest and hub genes, Gene Ontology and Pathway Analysis will be performed on each of these lists to establish which pathways are impacted in each comparison. The novel pathways for each arm comparison will guide our work towards specific mechanisms of action in COVID-19 patients. Mechanisms that vary between the arms of this study will also be identified by performing Gene Set Variation Analysis (GSVA)(6). This method generates a score for each pathway within the chosen pathway dataset, allowing for comparison of the pathways scores for each sample across the condition arms. This will be done using the linear modelling package limma. We will use the most recent release of pathway databases for this analysis, such as KEGG or Wikipathways.

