2.3.1 Differential Gene Expression analysis

Firstly, we will conduct outlier analysis using data visualization methods such as Principal Component Analysis, Boxplots, Hierarchical Clustering and IQR/Median plots. After testing for potential outliers, non-specific filtering will be conducted on our dataset to remove any very lowly expressed genes. Differential expression testing will be conducted in R version 4.1.2 using the Bioconductor package DESeq2(3). The data will be normalized with the DESeq2 mean of ratios method and baseline characteristics will be controlled for using the function design(model). We will first compare, for each drug arm, differentially expressed genes at pre-treatment versus post-treatment to understand the biological pathways driving drug response. We will modify our analysis as results evolve to test for differences in gene expression and identify transcriptomic gene signatures for genes and/or pathways driving differences between responders and non-responders for each drug. We will then compare gene expression between each treatment and SoC. We will also build smaller models comparing Differentially Expressed Gene (DEG) analysis between drug groups.

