2.6 Machine Learning

Machine learning integrates statistical and other mathematical techniques of function approximation and optimization to extract useful information from large and complex datasets. It offers algorithm for computational modelling to extract nonlinear relationship between covariates and responses, quantifying uncertainties in predictions, integrating multi-modal data and for dealing with changing environments such as drifts in population statistics. In this project, building on recent cutting-edge developments in the subject, with some of our own work in particular, we will use machine learning approaches to go beyond classic uses of statistics in bioinformatics for the analysis of the data. The primary goal will be the integrative analysis of gene expression observed at the transcriptomic and proteomic levels, as well as measurements of viral loads and responses to various treatments. We are mindful that the problem at hand is different from challenges such as automatic machine translation or computer vision used for self-driving cars which are characterized by the availability of very large corpora of data (in their millions) used in training very large models (sometimes in the billions of free parameters). The challenges here will be with relatively small amounts of data, carrying substantial uncertainty at levels of quantification and/or measurement and probably imbalanced when stratified by outcomes. Thus, we emphasize that the use of machine learning (expanded in the paragraphs below) is not to build predictive black-box models, but rather extracting useful relationships via the integration of the various sources of data mentioned above. To this end we will use machine learning for: (i) analysis by dimensionality reduction (e.g. Principal Component Analysis and other two dimensional visualization techniques that are robust; (ii) integrative analysis of multi-modal gene expression data (i.e. those genes whose transcript and protein level expressions are observed); (iii) formulation of outlier detection problems (as opposed to classification and regression problems to characterize measured responses; (iv) explore non-linear relationships by means of smallscale or highly regularized neural network models. The four parts will be heavily interlinked (e.g. dimensionality reduction may uncover small subspaces that can be used for efficient training of predictive models) and are not proposed as four sequential work-packages.

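### The cut-free pathway test (GSVA with limma) is stated only for differences between arms; for pre/post and responder contrasts, named pathways are tested only on lists of differentially expressed genes

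*Protocol*

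**What the plan says.** Section 2.3.1 of the Protocol sets out several DESeq2 contrasts: before versus after treatment within each drug arm, responders versus non-responders, each treatment versus standard of care (SoC), and smaller models between drugs. The responder work is meant to "identify transcriptomic gene signatures for genes and/or pathways driving differences between responders and non-responders for each drug".

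Section 2.3.3 then describes two kinds of pathway analysis.

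- **List-based.** "Following the identification of DEGs, gene modules of interest and hub genes", the plan says that "Gene Ontology and Pathway Analysis will be performed on each of these lists to establish which pathways are impacted in each comparison". The next sentence gives the results a role: "The novel pathways for each arm comparison will guide our work towards specific mechanisms of action in COVID-19 patients".
- **Score-based.** "Mechanisms that vary between the arms of this study will also be identified by performing Gene Set Variation Analysis (GSVA)(6". Of this method the plan says: "This method generates a score for each pathway within the chosen pathway dataset, allowing for comparison of the pathways scores for each sample". The scores are compared across arms with limma.

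The module lists do not come from a significance cut. Section 2.3.2 explains that "WGCNA is an unsupervised analysis method which clusters genes into defined modules". No DEG threshold, background gene set or RNA sample count per arm is stated.

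**The concern.** A DEG list reduces each gene's test statistic to in or out. A pathway can be found from the list only if enough of its genes pass a genome-wide criterion one at a time. When many genes in a pathway each move modestly in the same direction, the list may be nearly empty although the joint evidence is strong. A score computed on the whole pathway keeps that evidence.

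The Protocol has such a score but states it only for comparisons between arms. The pre/post contrast is meant to show which pathways drive drug response, and the responder contrast seeks pathways that separate outcomes within each drug. Neither has a stated score-based test. Section 2.6 itself warns that "The challenges here will be with relatively small amounts of data", so weak gene-level power is to be expected.

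A second risk lies in how results are read across drugs. Pathways found in each arm comparison are to steer the work on mechanisms, and no rule says that a drug-specific claim needs a direct comparison between drugs. A pathway on one list and absent from another may only reflect two noisy thresholds.

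**Working it through.** The Protocol gives no power, threshold or effect size for the pathway analysis, so there is no figure of its own to reproduce.

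**Group size.** Section 1.2.1.1: 286 − 14 = 272 samples. Section 2.3: three time points, four arms. With an even split (assumed), 272 / (3 × 4) = 22.7, about 23 per arm and day.

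**One gene.** For 23 v 23 and a shift of 0.5 SD, the expected z is 0.5 × √(23/2) = 1.70. Power is Φ(1.70 − z₁₋α/2): 0.40 at α = 0.05, 0.055 at 0.001 and 0.014 at 0.0001.

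**The list.** Take 6,000 genes, of which 5 sets × 50 = 250 are truly shifted. At p < 0.001 one expects 250 × 0.055 = 13.75 true and 5,750 × 0.001 = 5.75 false hits, a false share of 5.75 / 19.5 = 29%. At p < 0.0001 it is 0.575 / (3.5 + 0.575) = 14%. A 5% FDR therefore leaves almost nothing: the simulation below averaged about one DEG.

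**A pathway score.** The mean of 50 genes with correlation ρ has variance (1 + 49ρ)/50. For ρ = 0.05 this is 0.069 (SD 0.263) and the expected z is (0.5/0.263) × √(23/2) = 6.4 to 6.5. For ρ = 0.20 it is 0.216 (SD 0.465) and the expected z is about 3.6.

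**Simulation.** 6,000 genes; 60 sets of 50, of which 5 are shifted, all genes in the same direction; Benjamini–Hochberg (BH) at 5% for genes and for sets; 60 replicates per setting. The list method uses gene t-tests followed by hypergeometric over-representation. The score method is a t-test on the mean score per sample, a simple stand-in for GSVA with limma. Entries are the share of affected pathways found, list / score.

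| n per group | shift (SD) | ρ = 0.05 | ρ = 0.20 |
|---|---|---|---|
| 15 | 0.3 | 0% / 46% | 0% / 2% |
| 15 | 0.5 | 0% / 99% | 0% / 40% |
| 15 | 0.8 | 11% / 100% | 14% / 93% |
| 23 | 0.3 | 0% / 78% | 0% / 12% |
| 23 | 0.5 | 3% / 100% | 3% / 65% |
| 23 | 0.8 | 90% / 100% | 65% / 100% |
| 35 | 0.3 | 0% / 95% | 1% / 36% |
| 35 | 0.5 | 19% / 100% | 18% / 92% |
| 35 | 0.8 | 100% / 100% | 98% / 100% |

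**The two contrasts at issue** (100 sets of 50, ρ 0.05 to 0.15, 150 replicates):

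- Pre/post as 23 pairs, within-patient correlation 0.5 assumed. The expected gene z rises to 0.5 × √23 = 2.40. At 0.5 SD: list 14–17%, score 97–100%. At 0.7 SD: 93–99% v 100%.
- Responder split of 6 v 17 (assumed). At 0.5 SD: list 0%, score 13–62%. At 1.0 SD: 6–7% v 89–100%.

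The score declared null sets at about 0.2% each, so the gain is not bought with false positives.

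**Patterns that favour the list** (23 v 23, BH 5%). With only 10 of 50 genes shifted, by 1.2 SD, the list found 85–91% and a competitive test on all genes 3–17%. With all 50 shifted by 1.0 SD in mixed directions, the result was 100% v 0%.

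**Agreement between drugs.** For two drugs with the same true effect and a shared control (first simulation, 23 per group), the two results for an affected pathway disagreed in 20–31% of cases with lists and 0–1% with scores at 0.8 SD. At 0.5 SD and ρ = 0.20 the order reverses: 4% with lists, which found almost nothing for either drug, and 28% with scores.

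**The case against.** The strongest reply is that the plan already contains what is asked for. GSVA with limma uses no gene cut and covers the project's main question, drug against SoC and drug against drug. A reader might infer from the list sentence that all pathway testing rests on significance-filtered genes. The Protocol does not support that: GSVA stands in the same section, and modules and hub genes come from unsupervised clustering. Section 2.5 also correlates module eigengenes with clinical traits, which could pick up coordinated modest shifts. All this stands. But a data-driven module that is annotated afterwards is not a test of each named pathway in a given contrast, and the stated scope of GSVA remains differences between arms.

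Second, the main table assumes that every gene in a pathway shifts equally in one direction, which suits a score. With partial or mixed-direction regulation the list wins clearly. This stands too, and it rules out making a directional set test primary and demoting the lists.

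Third, the DEG threshold and the over-representation test were supplied for the calculation. Such details may properly sit in a statistical analysis plan, and their absence is not criticised here. The point concerns the scope that the Protocol gives to each method.

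Finally, a reader might suppose that pre/post contrasts have the smallest groups. Under an even split they have about the same 23 per arm and day, and pairing helps them. Only the responder splits are smaller.

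**Conclusion.** The point holds in a limited form. For pre/post and responder contrasts, the only stated test of named pathways is on DEG lists. With about 23 samples per group, that test finds roughly 3% of pathways whose genes shift together by 0.5 SD (14–17% if paired), while a score finds 65–100% (97–100% if paired). The gap largely closes by 0.7 SD with pairing. It stays wide for a 6 v 17 responder split even at 1.0 SD. At 0.3 SD with correlation 0.20 and 23 per group, the score is weak as well (12%).

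These figures rest on assumed arm sizes, effect sizes, correlations and FDR cut, on a mean score in place of GSVA, and on complete pairs. They show direction and order of size, not the trial's actual power.

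A reader might also infer that lists as such make identical drugs look different and that scores would cure this. The calculations do not support it: either method gives discordant results when its power is intermediate. They support the narrower rule that drug specificity needs a direct contrast. The point is a cheap improvement, not an error that invalidates the plan.

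**What to change.** In section 2.3.3:

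1. State that GSVA with limma, or a correlation-adjusted set test on all genes passing the expression filter, will be run for every contrast in section 2.3.1, including pre/post within arm and responders versus non-responders. Account for pairing within patient in pre/post, and control the FDR across sets.
2. Keep the ontology and pathway analysis of DEG, module and hub-gene lists alongside it, not as a replacement and not replaced by it.
3. State that a pathway will be called specific to one drug only when the direct between-drug limma contrast of its score supports this, and not because it is on one drug's list and absent from another's.

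The cost is a few sentences and a short additional step on existing data. The downsides are a little more analysis, more tests to control for multiplicity, and possibly fewer pathways called drug-specific.

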NIHR150393: Exploring and grouping COVID-19 pharmaceutical interventions to determine mechanisms of action and endotypes of response

This project is funded by the NIHR Efficacy and Mechanism Evaluation (EME) Programme (NIHR150393). The views expressed in this protocol are those of the author(s) and not necessarily those of the NIHR, NHS England or the Department of Health and Social Care

1 Research design

This research project is designed to identify the biological mechanisms through which novel COVID-19 drugs provide therapeutic benefit using data obtained from the ACCORD clinical trial(1). We will compare three novel therapeutics (Bemcentinib, Tozorakimab (previously known as MEDI3506) and Zilucoplan) to the Standard of Care (SoC) for severe COVID-19 patients using multiple data types (transcriptomics, proteomics, viral load, and pharmacokinetic drug levels). Each COVID-19 drug will be compared to the SoC of care individually before comparing the identified biological mechanisms comparatively to compare the mechanisms and conditions being modulated favourably by these drugs. Additionally, we will explore biological mechanisms and differences and relationships to effect size of clinical response as measured by time to improvement or discharge. This will better help us understand how the novel drugs work and how to select efficient treatments for a particular patient

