1.1 Study Population

The inclusion criteria for the ACCORD trial were:

Adults (>= 18 years) with SARS-CoV-2 infection confirmed by laboratory tests and/or point of care tests. Patients must be scored between Grade 3 (hospitalised – mild disease, no oxygen therapy) to Grade 5 (hospitalised - severe disease, non-invasive ventilation or high flow oxygen) on ACCORD's 9 point WHO ordinal scale from clinical improvement (OSCI) where Grade 0 is uninfected and 8 is death. Overall, in the ACCORD study 167 subjects were randomised, 14 subjects withdrew and 25 subjects died. In the additional Bemcentinib study, a further 115 were randomised – 60 to SoC and 55 to Bemcentinib in an identical study design.

1.2 Sampling.

Samples from patients were collected in line with the sample collection schedule below:

	Baseline								
Day	1	3	4	5	8	10	11	15	29
Biological sample type									
Blood (for RNA)	Х			Х		Х			
Blood (for serology)	Х							Х	
Blood (for protein)	Х			Х		Х			
Oropharyngeal swab (for viral load)	Х	Х		Х	Х		Х	Х	Х
Pharmacokinetic drug concentration									
Bemcentinib	Х		Xa		Х			Х	
Tozorakimab	Xb							Xc	
Zilucoplan	Х			Х		Х		Х	

Table showing the sample collection schedule for the ACCORD COVID-19 clinical trial.

Adapted from (1) to show only the samples collected to generate the datasets relevant to this current project. X = sample collected. All patients were sampled on day 1, which is considered baseline prior to the first dose of the assigned treatment arm or standard of care. Each drug had slightly different pharmacokinetic (PK) sampling regimes and were mostly collected predose. Where samples for PK were collected other than pre-dose, collection information is detailed below:

- ^a Sample collected pre-dose and 6 hours post-dose (Day 4).
- ^b Sample collected pre-dose and 15 minutes post-dose (Day 1).
- ^c Sample collected pre-dose and 15 minutes post-dose (Day 15).

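### Drug-specific mechanisms are approached by comparing separate drug-versus-SoC findings, and the planned direct between-drug contrasts do not decide which mechanisms count as specific

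*Protocol*

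**What the plan says.** Protocol section 1 (Research design) fixes the order of inference: "Each COVID-19 drug will be compared to the SoC of care individually before comparing the identified biological mechanisms comparatively". What enters the second step is therefore whatever the first step identified.

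Section 2.3.3 carries this out for pathways. Enrichment is run on the differentially expressed genes, hub genes and gene modules: "Gene Ontology and Pathway Analysis will be performed on each of these lists to establish which pathways are impacted in each comparison". Its use is stated in the sentence that follows: "The novel pathways for each arm comparison will guide our work towards specific mechanisms of action in COVID-19 patients". No contrast between drugs, estimate or interval is attached to that step.

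Direct comparisons are planned too:

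- Section 2.3.3 continues: "Mechanisms that vary between the arms of this study will also be identified by performing Gene Set Variation Analysis (GSVA"), with limma, "allowing for comparison of the pathways scores for each sample across the condition arms".
- Section 2.3.1 says: "We will also build smaller models comparing Differentially Expressed Gene (DEG) analysis between drug groups". This could mean a direct contrast or a comparison of two sets of results.
- Section 2.3.4 adds a multigroup splicing analysis across the drug arms, after pairwise pre/post and drug-versus-SoC comparisons.

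Section 2.4 (proteins) names two kinds of test: each drug against SoC, and responders against non-responders within a drug arm. It names no drug-versus-drug test.

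**The concern.** Absence of a pathway from a drug's list means only that it did not pass that comparison's threshold. In small arms this happens often even when the effect is real. If two drugs act on a pathway to the same extent, chance alone will often put it on one list and leave it off the other. Comparing the lists then suggests a difference in mechanism that the data do not support.

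This matters because the project title promises to group interventions by mechanism, and section 1 describes the second step as "before comparing the identified biological mechanisms comparatively to compare the mechanisms and conditions being modulated favourably by these drugs". Deciding whether drugs share or differ in mechanism is the aim, not a by-product. The protocol also gives no rule for conflict between the two routes, for example when the lists separate two drugs and the GSVA scores do not.

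**Working it through.** **No plan figure to reproduce.** The protocol gives no alpha, effect size or number of RNA samples per arm for these comparisons. The one related sum is correct: 286 − 14 = 272 retained samples (section 1.2.1.1).

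**Inputs.** Section 2.3 gives three time points and four arms (three drugs and SoC). If the samples are spread evenly, which is an assumption, 272 / (3 × 4) = 22.7, or about 23 patients per arm per time point. Also assumed: one pathway score per patient with SD 1, the same true effect d for every drug, one shared SoC arm, and two-sided tests.

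**Power of one drug-versus-SoC test.** Power ≈ Φ(d / √(2/n) − z). With n = 23, √(2/23) = 0.295, and z = 1.96 at alpha 0.05:

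- d = 0.5: 0.5 / 0.295 = 1.70, and Φ(1.70 − 1.96) = 0.40
- d = 0.8: 0.8 / 0.295 = 2.71, and Φ(2.71 − 1.96) = 0.77
- d = 1.0: 1.0 / 0.295 = 3.39, and Φ(3.39 − 1.96) = 0.92

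**How often two identical drugs disagree.** If each drug had its own SoC arm, the probability that exactly one is significant would be 2p(1 − p). At d = 0.5 that is 2 × 0.396 × 0.604 = 0.48. A shared SoC arm correlates the two tests and lowers this, so the shared-arm case was simulated (400,000 runs per setting, normal approximation). The table gives the percentage of cases in which two given drugs differ in significance although their true effects are equal.

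| Per arm | Alpha | d = 0.5 | d = 0.8 | d = 1.0 | Direct drug-versus-drug test |
|---|---|---|---|---|---|
| 15 | 0.05 | 28% | 32% | 24% | 5% |
| 23 | 0.05 | 32% | 24% | 11% | 5% |
| 30 | 0.05 | 33% | 16% | 4.5% | 5% |
| 23 | 0.001 | 8% | 28% | 33% | 0.1% |

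A separate simulation with t-tests at 23 per arm and d = 0.5 also gave 32% disagreement, with power of 38%.

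**Why the direct contrast holds its level.** In the difference of the two drug-minus-SoC effects the shared SoC mean cancels. With equal true effects the remaining statistic has mean zero, so it rejects at the nominal rate whatever d is.

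**Reading the table.** Disagreement is greatest when power is middling and falls to the level of the direct test only when power is very high (30 per arm, d = 1.0, alpha 0.05). A stricter alpha does not cure it: at 23 per arm and d = 1.0, moving from 0.05 to 0.001 raises disagreement from 11% to 33%.

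**The case against.** The strongest reply is that the protocol never draws the faulty inference. A reader might infer that non-significance in a small arm is being taken as proof that a mechanism is absent. The text does not say so: the lists only guide further work, and the project is exploratory. That part of the reply stands. The word 'novel' is also ambiguous; it may mean newly found rather than unique to one comparison. But section 1 still sets the sequence of identifying per drug and then comparing what was identified.

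Second, direct analysis is already planned, and GSVA with limma across arms is close to the remedy. This stands as a description. However, it is introduced as an additional route, and nothing makes it decide what is drug-specific. For proteins no direct test is named.

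Third, such a rule might be left to a statistical analysis plan. That would be fair if the protocol were silent, but it fixes the order of comparisons itself.

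Fourth, the calculation uses one score per patient, whereas the criticised route is enrichment of gene lists. It also ignores repeated time points and baseline adjustment. This is correct, and the percentages are illustrations only.

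A reader might also infer that bemcentinib would appear to have more unique mechanisms because of the additional study, in which "a further 115 were randomised – 60 to SoC and 55 to Bemcentinib in an identical study design". The document does not say whether those patients supplied RNA samples, so that claim is not supported.

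**Conclusion.** The point holds as a weakness in method. It is not a contradiction in the protocol, nor a claim by the protocol that non-significance proves absence. Comparing per-drug findings carries no test of a difference between drugs, and the direct analyses that would supply one do not govern the conclusion.

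Under the stated assumptions (23 per arm, one score per patient, shared SoC, equal true effects, alpha 0.05), two identical drugs are separated in about 32% of cases at d = 0.5 and 24% at d = 0.8, against 5% for a direct contrast. Over 15 to 30 per arm and d from 0.5 to 1.0 at the same alpha, the range is 4.5% to 33%. Arm sizes, effects and alpha are assumptions, and list enrichment was not simulated. The change is cheap and should be made.

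**What to change.** In section 2.3.3, state that a pathway is called specific to one drug only when the direct contrast between the drugs is significant after multiplicity correction. The contrast is the difference of the two drug-minus-SoC effects, taken from the planned limma model on GSVA scores with all arms included. Otherwise report the pathway as 'not distinguished', with both drug-minus-SoC estimates and their confidence intervals. Use the per-drug lists only to generate candidates. Apply the same rule to the proteins in section 2.4, through an equivalent direct between-drug comparison. Reword the sentence on between-drug expression models in section 2.3.1 so that it is clear whether a direct contrast is meant.

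The cost is one rule in the text and one contrast in a model already planned; no new data are needed. The downside is low power. By the formula above, with 23 per arm a direct contrast misses a true drug difference of 0.5 SD about 60% of the time at alpha 0.05 and about 94% at alpha 0.001. Fewer mechanisms will be called drug-specific, so the 'not distinguished' category must not be read as evidence that the drugs are the same.
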